### 15.5.3. Reporting Standards for Pharmacokinetic

Pharmacokinetic Concentration Data	
PC Windows Non-Linear (WNL) File	PC WNL file (CSV format) for the non-compartmental analysis by Clinical Pharmacology Modelling and Simulation function will be created according to GUI_51487.  Note: Concentration values will be imputed as per GUI_51487.
Descriptive Summary Statistics, Graphical Displays and Listings	Refer to IDSL PK Display Standards. Refer to IDSL Statistical Principle 6.06.1.  Note: Concentration values will be imputed as per GUI_51487 for descriptive summary statistics/analysis and summarized graphical displays only.
NONMEM/Pop PK File	Pop-PK file (CSV format) for the POP-PK analysis by Clinical Pharmacology Modelling and Simulation function will be created according to the data specification (separate document).
NONMEM/PK/PD File	PK/PD file (CSV format) for the PK/PD analysis by Clinical Pharmacology Modelling and Simulation function will be created according to the data specification (separate document).
Pharmacokinetic Parameter Derivation	
PK Parameter to be Derived by Programmer	No PK parameters will be derived by the Programmer
Pharmacokinetic Parameter Data	
Is NQ impacted PK Parameters Rule Being Followed	Yes, refer to SOP_314000 [Standards for Handling NQ Impacted PK Parameters].
Descriptive Summary Statistics, Graphical Displays and Listings	Refer to IDSL PK Display Standards. Refer to GUI_51487.

## 15.6. Appendix 6: Derived and Transformed Data

This appendix describes how data are derived for further reporting. In general, these instructions apply at the participant level prior to any summaries being created.

### 15.6.1. General

Multiple Measurements at One Analysis Time Point	

 
Mean of the measurements will be calculated and used in any derivation of summary statistics but if listed, all data will be presented.
 
Participants having both High and Low values for Normal Ranges at any post-baseline visit for safety parameters will be counted in both the High and Low categories of “Any visit post-baseline” row of related summary tables. This will also be applicable to relevant Potential Clinical Importance summary tables.
 
	
Study Day	

 
Calculated as the number of days from First Dose Date: 
 
Ref Date = Missing → Study Day = Missing
 
Ref Date < First Dose Date → Study Day = Ref Date – First Dose Date
 
Ref Date ≥ First Dose Date → Study Day = Ref Date – (First Dose Date) + 1
 
 
 
	

### 15.6.2. Study Population

Exposure
Partial Doses

 
For partial IV doses, the quantity of IP given to the participant will be calculated using the simplifying assumption that IP is dosed at a constant rate using the following formula:  IP dose received = IP dose expected * ((dose stop time – dose start time) / expected duration of dosing) 
 
Section 5.1.2 shows the expected duration of dosing which is dependent on visit.
 
For partial SC doses, the quantity of IP given to the participant will be calculated based on the number of injections received. The expected SC dose is always two injections (2 x 150mg) so a single injection will dose 150mg.
 

Number of Doses
Summarise the number of doses received by participants within each study phase.
Cumulative Dose
The cumulative received dose in mg will be calculated across all phases and within each study phase for each participant.
Duration of Exposure

The number of days of exposure will be calculated for each participant within study phase and across all study phases.
 
 
The following algorithm will be used for calculating days exposed across all study phases:
 
 $\text{Duration of Exposure} = \text{Last dose date} - \text{first dose date} + 1$

2. The following algorithm will be used for calculating days exposed in a study phase:

$$\text{Duration of Exposure} = \text{Last dose date of phase} - \text{first dose date of phase} + 1$$

Note: subjects with multiple missed doses in a phase are not expected to start the next phase.

#### **Smoking History: Pack years**

- Pack years = (number of daily cigarettes / 20) x number of years smoked
  - If frequency reported is weekly; number of daily cigarettes = weekly cigarettes x 7 days
  - If frequency reported is monthly; number of daily cigarettes = monthly cigarettes x 30.44 days

### **15.6.3. Efficacy**

#### **15.6.3.1. Mayo score versions**

All Mayo scores are the sum of the components. The number of components and their definition vary as described below and will be derived programmatically. Stool Frequency and Rectal Bleeding will be derived from eDiary data.

#### **Complete 4-Domain Mayo Clinic Score (MCS)**

Sign/Symptom	Score	
	CCI	
CCI - This section contained Clinical Outcome Assessment data collection questionnaires or indices, which are protected by third party copyright laws and therefore have been excluded.		

**Complete 4-Domain Mayo Clinic Score (MCS)**

The Complete Mayo score (sum of four components, range 0-12) includes a physician global assessment, and **CCI** at endoscopy contributes to an endoscopic score of **CCI**. The following categorical endpoints are derived from this score:

- **Clinical remission (Complete Mayo)** is defined as: Complete MCS  $\leq 2$ , with no individual sub-score  $> 1$
- **Clinical response (Complete Mayo)** is defined as: Reduction in complete MCS  $\geq 3$  points from baseline **AND**  $\geq 30\%$  from baseline **AND** decrease in the rectal bleeding sub-score of  $\geq 1$  point from baseline (or a score of 0 or 1)
- **Symptom Control** for rectal bleeding is defined as a sub-score of 0
- **Symptom Control** for stool frequency is defined as a sub-score of 0 or 1 with no worsening from baseline
- **Symptomatic Remission** is defined as **Symptom Control** for both rectal bleeding and stool frequency

**Partial Mayo Clinical Score**

Sign/Symptom	Score
CCI	

CCI - This section contained Clinical Outcome Assessment data collection questionnaires or indices, which are protected by third party copyright laws and therefore have been excluded.

The Partial Mayo Clinical Score (sum of three components, range 0-9) is based on the complete 4-domain MCS, but without the endoscopy sub-score

- The definitions of **Clinical Remission (Partial Mayo)** and **Clinical Response (Partial Mayo)** are the same as described for complete Mayo with the baseline being the partial Mayo score instead of the complete Mayo score. Note that the baseline visit for the Partial Mayo score differs from Complete and Adapted.

## Adapted 3-domain Mayo Clinical Score

Sign/Symptom	Score	
	CCI	
CCI - This section contained Clinical Outcome Assessment data collection questionnaires or indices, which are protected by third party copyright laws and therefore have been excluded.		

The Adapted 3-domain Mayo Clinical Score (sum of three components, range 0-9) is based on the complete 4-domain MCS, but without the physician global assessment and with an alternative definition of the endoscopy scores. The following categorical endpoints are derived from this score:

- **Clinical Remission (Adapted Mayo)** is defined as adapted MCS of <=2 with no individual sub-score > 1 and a rectal bleeding sub score of 0 with stool frequency sub score not greater than baseline.
- The definition of **Clinical Response (Adapted Mayo)** is the same as described for complete Mayo with the baseline being the adapted Mayo score instead of the complete Mayo score
- The definition of **Clinical Remission (FDA)** requires an absolute stool number of 3 or fewer (*average daily stool number during 3 days before a visit*), a Mayo rectal bleeding sub-score of 0, and an adapted Mayo endoscopic sub-score of 0 or 1.
- **Endoscopic Remission** is defined as: **Adapted Mayo** endoscopic score = 0
- **Endoscopic Improvement** is defined as: **Adapted Mayo** endoscopic score = 0 or 1, this endpoint is also referred to as '**Endoscopic Mucosal Healing**' in the project.

Extended Treatment Phase endpoints:

- **Steroid Free Clinical Remission** will be reported at Week 30 only. It is defined as **Clinical Remission (Adapted Mayo)** at Week 30 **AND** participant has not received a steroid dose in the 28 days prior to the day of the efficacy assessment.
- **Maintained Steroid Free Clinical Remission** will be reported at Week 42 only. It is defined as participants who were in **Steroid Free Clinical Remission** at Week 30 **AND** who are in **Clinical Remission (partial Mayo)** at Week 42 (follow up) **AND** that did not receive any dose of steroid between Week 30 and Week 42.
- **Maintained Clinical Response (Week 10 to 30 Adapted Mayo)** will be reported at Week 30 only. It is defined as **Clinical Response (Adapted Mayo)** at Week 10 **AND** **Clinical Response (Adapted Mayo)** at Week 30.

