10.7. Appendix 7: Mayo Clinic Score Definitions

*Complete 4-domain Mayo Clinic Score (MCS)**

CCI - This section contained Clinical Outcome Assessment data collection questionnaires or indices, which are protected by third party copyright laws and therefore have been excluded.

Clinical remission: Complete MCS ≤ 2 , with no individual subscore > 1 .

Clinical response: Reduction in Complete MCS ≥ 3 points from baseline **AND** $\geq 30\%$ from baseline **AND** decrease in the rectal bleeding subscore of ≥ 1 point from baseline (or a score of 0 or 1).

*Partial MCS**

CCI - This section contained Clinical Outcome Assessment data collection questionnaires or indices, which are protected by third party copyright laws and therefore have been excluded.

CCI

Clinical remission: Partial MCS ≤ 2 , with no individual subscore > 1 .

Clinical response: Reduction in partial MCS ≥ 2 points from baseline **AND** $\geq 30\%$ from baseline, **AND** a decrease in the rectal bleeding score of ≥ 1 point from baseline or a score of 0 or 1.

*Adapted 3-domain MCS**

CCI - This section contained Clinical Outcome Assessment data collection questionnaires or indices, which are protected by third party copyright laws and therefore have been excluded.

Clinical remission: Adapted MCS of ≤ 2 with no individual subscore > 1 , a rectal bleeding subscore of 0, and stool frequency subscore ≤ 1 and not greater than baseline.

Clinical response: Reduction in adapted MCS ≥ 2 points from baseline **AND** $\geq 30\%$ from baseline, **AND** a decrease in the rectal bleeding score of ≥ 1 point from baseline or a score of 0 or 1.

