#### 2.1.3. Changes to Endpoints and Definitions

##### 2.1.3.1. Efficacy

Exploratory efficacy endpoints (excluding Serum C-Reactive Protein and Faecal Calprotectin) are documented in the protocol, but their analysis is not covered in this RAP due to the termination of the study.

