**Footnotes:**

[figure not shown]
- 1 Potential clinical importance is defined in Section 15.8 for each relevant safety endpoint.
- 2 The Complete 4-domain Mayo score is used for the primary endpoint due to its wider dynamic range for assessment of dose-response compared to the Adapted Mayo score used for secondary and exploratory endpoints.
- 3 Clinical response and remission for the various iterations of Mayo score are defined in [Appendix 7](#), Section 15.7.
- 4 Symptomatic remission is defined as a rectal bleeding subscore of 0, and a stool frequency subscore of  $\leq 1$ , with no worsening from baseline.
- 5 Taper period is defined from the start of the taper (Weeks 12 or 24, respectively, for the Double-Blind and Open Label Extended Treatment Phases) to completion of the respective Extended Treatment Phases.

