#### 8.2.2. Other Secondary Endpoints - Categorical

The ICE strategy for the Key Secondary Estimand described in Section 8.2.1.1 above will be replicated in the following secondary Efficacy endpoints:

Endpoint	Endpoint name to be displayed for Estimand Analysis
Adapted Mayo Clinical Remission at Week 10	Secondary – Adapted Mayo Clinical Remission
Adapted Mayo Clinical Response at Week 10	Secondary – Adapted Mayo Clinical Response
Symptomatic Remission at Week 10	Secondary – Symptomatic Remission

The “Secondary Estimand – Clinical Remission” will be analysed by replicating the statistical model described in Section 8.2.1.2 above. The other two estimands in the table above will be summarised only.

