## CONFIDENTIAL

204869

Efficacy: Tables					
No.	Population	IDSL / Example Shell	Title	Programming Notes	Deliverable [Priority]
2.23.	ITTE	EFF_T3	Statistical Analysis of Dose Response Relationship for Categorical Endpoints	
By Endpoint then estimand.
 
 
• Endoscopic Improvement (IA4 and PC)
 
• Endoscopic Improvement, Clinical Response, Clinical Remission, ( PC only)
 
• Present analysis results for both 'Treatment Policy' and 'Hypothetical' estimands if conducted
 
	None
Histological assessments					
2.24.	ITTE	EFF_T2	Summary of Categorical Histology at each Dose Level by Endpoint in Induction Phase	
Report by endpoint, visit.
 
Geboes Histological Remission
 
RHI Remission
 
RHI Deep Remission
 
Nancy Index Remission
	SAC
2.25.	ITTE ETP	EFF_T2	Summary of Categorical Histology by Endpoint in Extended Treatment Phase	Report by endpoint, visit.	None

Efficacy: Tables					
No.	Population	IDSL / Example Shell	Title	Programming Notes	Deliverable [Priority]
Extra Intestinal Manifestations					
2.26.	ITTE	EFF_T4	Summary of Extra Intestinal Manifestations (EIMs) - Incidents by Severity, across Study Phases.	For EIMs without severity (Peripheral Arthritis and Axial Arthropathy) set levels of severity to missing  Slot early withdrawal visits to next EIM visit (there is one EIM visit at the end of each study phase)  Summary is cross-phase: Report by treatment sequence, not by treatment in an individual study phase	None
Continuous Efficacy – Pairwise Statistical Analysis					
2.27.	ITTE	EFF_T5	Statistical Analysis of Change from Baseline in Complete Mayo Score in Induction Phase		IA3H
Summaries of Efficacy after Estimand Imputations					
2.28.	ITTE	EFF_T2	Summary of Categorical Efficacy by Endpoint in Induction Phase - Estimands		IA3H, SAC
2.29.	ITTE	PD1	Summary of Mayo Score by Endpoint in Induction Phase - Estimands		SAC
2.30.	ITTE	PD1	Summary of UCEIS Total Score in Induction Phase - Estimands		SAC

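### The SAP applies the Complete Mayo 3-point cut to Adapted and Partial Mayo clinical response, where protocol Appendix 7 uses 2 points, and does not declare the change

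*SAP*

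**What the plan says.** **Protocol, Section 10.7 (Appendix 7).** Three versions of clinical response are written out separately. The Complete version needs a fall of at least 3 points. The Partial and Adapted versions need at least 2; the Adapted one begins "Clinical response: Reduction in adapted MCS". All three add a fall of at least 30% from baseline and a rectal bleeding condition (a drop of at least 1 point, or a score of 0 or 1).

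**SAP, Section 15.6.3.1.** The Complete definition, beginning "Reduction in complete MCS", agrees with the protocol at 3 points. The other two are not written out. Adapted response "is the same as described for complete Mayo with the baseline being the adapted Mayo score instead of the complete Mayo score". Partial remission and response "are the same as described for complete Mayo with the baseline being the partial Mayo score instead of the complete Mayo score".

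**Declared changes.** SAP 2.1.3.1 is where changes to efficacy endpoints and definitions are listed. Its only entry concerns exploratory endpoints, of which it says "their analysis is not covered in this RAP due to the termination of the study". SAP 2.1.4 covers estimands and models. Neither mentions a response threshold.

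**Use of the endpoint.** Adapted Mayo clinical response at Week 10 is a secondary endpoint in both documents. SAP 8.2.2 keeps it, gives it an estimand name, models only clinical remission, and adds: "The other two estimands in the table above will be summarised only".

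**The concern.** Read literally, the SAP moves a 3-point cut from a 12-point scale onto two 9-point scales. The SAP says Mayo scores are derived programmatically, so a programmer working from it would code 3 points. The report would then give a secondary endpoint under the protocol's name but with a stricter rule, and a reader holding the protocol would not know.

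There is also a coherence problem. Adapted remission and Adapted response are both to be summarised at Week 10. Under the protocol, everyone in remission is also a responder. If the response cut is raised and the remission rule is left alone, that ordering can fail.

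**Working it through.** No sample size, power or decision figure in the documents rests on this definition, so there is no stated figure to reproduce. The check is textual first, then arithmetic.

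**1. Does anything in the SAP restore the 2-point cut?**
- SAP 2.2 footnote 3 says "Clinical response and remission for the various iterations of Mayo score are defined in" Appendix 7, Section 15.7. In the protocol, Appendix 7 holds the Mayo definitions. In the SAP, Section 15.7 is the missing-data appendix, so the pointer leads nowhere useful.
- The closing text of SAP 8.2.3.1 sends the reader to Section 15.6, which contains the 3-point wording.
- No 2-point response cut appears anywhere in the SAP.

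**2. Minimum fall needed for Adapted response.** For integer scores and baseline b, the minimum fall is max(cut, 0.30 × b rounded up), with cut = 2 (protocol) or 3 (SAP).

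| Baseline b | 0.30 × b | 2-point fall as % of b | Minimum fall, protocol | Minimum fall, SAP |
|---|---|---|---|---|
| 3 | 0.9 | 67% | 2 | 3 |
| 4 | 1.2 | 50% | 2 | 3 |
| 5 | 1.5 | 40% | 2 | 3 |
| 6 | 1.8 | 33% | 2 | 3 |
| 7 | 2.1 | 28.6% | 3 | 3 |
| 8 | 2.4 | 25% | 3 | 3 |
| 9 | 2.7 | 22% | 3 | 3 |

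At baseline 3 the SAP rule requires a final score of 0.

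**3. Which baselines can occur?** Protocol 5.1 requires a Complete score of 6 to 12, endoscopy at least 2 and rectal bleeding at least 1. The score tables are redacted, so two assumptions are needed: subscores are integers 0 to 3 (which fits 12 points over four domains and 9 over three), and an endoscopy subscore of 2 or 3 is the same on the Adapted scale. Then 2 endoscopy × 3 bleeding × 4 stool values = 24 baseline triples, each compatible with some physician global score. Adapted totals run from 3 to 9, with 1, 3, 5, 6, 5, 3 and 1 triples respectively. Baselines 3 to 6 account for 1 + 3 + 5 + 6 = 15 of the 24.

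**4. Both rules applied to every profile.** Crossing the 24 baselines with all 4³ = 64 possible Week 10 triples gives 24 × 64 = 1,536 profiles.

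| Baseline | Responders, 2-point cut | Responders, 3-point cut | Difference |
|---|---|---|---|
| 3 | 4 | 1 | 3 |
| 4 | 27 | 12 | 15 |
| 5 | 83 | 46 | 37 |
| 6 | 150 | 102 | 48 |
| 7 | 127 | 127 | 0 |
| 8 | 104 | 104 | 0 |
| 9 | 44 | 44 | 0 |
| Total | 539 | 436 | 103 |

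All 103 differences are falls of exactly 2 points. None goes the other way.

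**5. Remission against response.** Adapted remission needs endoscopy 0 or 1, bleeding 0, and stool 0 or 1 and no higher than baseline. The 6 baselines with stool 0 each allow 2 remission outcomes (12). The 18 with stool 1 or more each allow 4 (72). The total is 84. Non-responders among them number 0 under the 2-point cut and 2 under the 3-point cut. Written as endoscopy/bleeding/stool, the two are 2/1/0 to 1/0/0 (total 3 to 1) and 2/1/1 to 1/0/1 (total 4 to 2).

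**6. Partial Mayo.** The minimum-fall table is the same: the rules differ at baselines 3 to 6 and agree at 7 to 9.

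**The case against.** The strongest reply is about consequence. The study was terminated, the endpoint is only summarised, and no model, primary or key secondary result, sample size or futility rule uses it. Partial response enters only exploratory open-label endpoints whose analysis the SAP drops, and maintained response is exploratory with its display removed. Baseline values are not equally likely, so four affected values out of seven says little about participants. The remission anomaly rests on 2 of 84 hypothetical profiles: one needs a physician global score of 3 to be eligible, the other at least 2. All of this stands, and it limits the weight of the point.

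The displays are also less definite than they look. The observed-data table of categorical endpoints (Table 2.17) omits clinical response. The estimand table, titled "Summary of Categorical Efficacy by Endpoint in Induction Phase - Estimands" (Table 2.28), and Figure 2.9 list no endpoints. The commitment to report response therefore rests on SAP 8.2.2, and these two displays are only where it would be expected to appear.

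Finally, Week 10 responder status, which routes participants to the next phase, is calculated in the eCRF, and the protocol refers to its own Appendix 7 for it. The SAP sentence does not govern that routing.

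None of these points reconciles the two definitions or supplies a declaration of the change.

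**Conclusion.** The point holds and should be fixed. For a retained secondary endpoint, the SAP's rule is stricter than the protocol's, and the difference is not declared. It bites only at Adapted baselines 3 to 6, for a fall of exactly 2 points with the bleeding condition met, and it can only lower the response count in either arm. It also permits remission without response, which the protocol rule does not.

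The counts in the working are score profiles under the stated subscore assumptions, not participant rates. The documents give no distribution of baseline Adapted scores, so the change in the response rate cannot be estimated. The mismatch itself is plain from the text and does not depend on those assumptions.

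**What to change.** In SAP 15.6.3.1, write out Adapted and Partial clinical response as in protocol Appendix 7: at least 2 points, and at least 30% from baseline, and the rectal bleeding condition. Keep 3 points for Complete Mayo only. If the stricter cut is intended, state and justify it in SAP 2.1.3 instead. Either way, point SAP 2.2 footnote 3 to Section 15.6.3.1. It would also help to name Adapted clinical response among the endpoints of Table 2.28 and Figure 2.9.

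The cost is two sentences, one cross-reference and one derivation line. Both displays are also scheduled for the Interim Analysis 3 headline delivery. If response was shown there under the 3-point rule, a short note is needed to explain why the final count differs.

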**Adapted 3-domain Mayo Clinical Score**

- **Maintained Clinical Remission (Week 10 to 30 Adapted Mayo)** will be reported at Week 30 only. It is defined as **Clinical Remission (Adapted Mayo)** at Week 10 **AND Clinical Remission (Adapted Mayo)** at Week 30.

**15.6.3.2. Mayo sub scores**

Mayo sub scores will be derived from the daily eDiary. For each calculated Mayo score the following steps are required:

- Select days to be used as source data from the previous seven.
- Calculate Stool Frequency sub-score (derived from relevant daily stool counts)
- Calculate Rectal Bleeding sub-score (simple average of relevant daily entries)
- Calculate Absolute Stool Number (simple average of relevant daily stool counts)

**Day selection algorithm**

The eDiary should be used daily and should not allow a participant to save partial data (i.e. if an entry for stool count is available, then an entry for rectal bleeding should also be available), it is therefore assumed that both Stool Frequency and Rectal Bleeding will be present on a specific day, or both will be missing.

The scores reflect a patient's experience over an entire day and so can only be calculated once the day is complete. The previous day's score is therefore used at a study visit (i.e. entered into the eCRF by the site) but by contrast, the eDiary will be analysed after all data has been collected and so the daily sub-score will be reported against the latest study day in the window of possible days (the 'named day'). When daily sub-scores are presented they use the named day, for example daily sub-scores reported at study Day 1 will include the day of the first dose of IP (Day 1) but the (Partial) Mayo score reported at the Day 1 visit will use the value from Day -1 for consistency with the value recorded by the site and general practice in using the Mayo score. This reporting of daily sub-scores is consistent with practice in the literature ([Hanauer, 2019](#)).

Considering the last 7 days (including the named day) exclude any days where a participant:

- Received bowel preparation medication for an endoscopy
- Had an endoscopy
- Is the day after an endoscopy

From the remaining days, working backwards from the most recent available day, use the following hierarchy to select the most appropriate days:

1. Three consecutive days of data, as close to the endoscopy visit as possible.
2. If three consecutive days are not available, three non-consecutive days of data, as close to the endoscopy visit as possible.
3. If fewer than three days' data are available in the prior seven days, set both SF and RB sub-scores to missing.

See the table at the end of the 'Rectal Bleeding' section for examples of day choice in different circumstances.

Note that the following alternative algorithm will also be calculated for sensitivity analyses:

[figure not shown]
1. Three consecutive days of data, as close to the endoscopy visit as possible.
2. If three consecutive days are not available, three non-consecutive days of data, as close to the endoscopy visit as possible.
3. If fewer than three days' data are available in the prior seven days, use data from the two most recent days.
4. If fewer than two days' data are available in the prior seven days, set both SF and RB sub-scores to missing.

If there is a greater than 5% difference between the number of participants in the main algorithm and in the sensitivity algorithm (i.e. participants with only two days at Day 1 or Week 10), then a sensitivity analysis will be run.

